The infectious disease trained pharmacist may use pharmacokinetic software to analyse drug concentration-time profile to guide dose adjustments. If available, dose recommendations will be based on the MIC of the known pathogen, which will be provided by the local microbiology laboratory. Where no pathogen was formally identified, MICs are not available or cultures are pending, the highest MIC (according to the Clinical and Laboratory Standards Institute (CLSI criteria) for susceptible bacteria to the antibiotic will be assumed.

Data Collection

All patients will be followed up from study entry to 30 days from study entry, hospital discharge or mortality, whichever occurs earlier.

Data will be collected from electronic medical records, using a standardised data collection form. These will include:

•patient demographics (unique identifier, age, gender, race, body weight, height, comorbidities including Charlson Comorbidity Index)

•pharmacokinetic-specific data (use of extracorporeal therapy/dialysis and settings, urine output, serum creatinine, albumin)

•clinical data (temperature, blood pressure, heart rate, respiratory rate, mortality, cause of mortality, severity of illness indicators such as APACHE II score and SOFA score, incidence of beta-lactam-related adverse events/side effects as reported by primary physicians, admission and discharge date from hospital and from intensive care unit if applicable)

•laboratory data (albumin, serum creatinine, procalcitonin, CRP, total white count)

•infection-related data (site and type of infection, pathogens isolated and their susceptibility results and reported minimum inhibitory concentrations)

•drug-related data (beta-lactam dosing regimens including any change to dosing regimens, concurrent antibiotic use history and their dosing regimens, presence of any drug which may interact with beta-lactams or interfere with beta-lactam assay results)

•beta-lactam assays levels, attainment of therapeutic targets and whether dose adjustments were made

Data will be stored in a password-protected database and only study team members will have access to data. Identifiers will be stored separately from collected data. Data collection forms will not contain identifiers (e.g. NRIC, name, date of birth). All hardcopy data collection forms and consent forms will be stored under lock and key in the cupboard at [name] of

Pharmacy department in Singapore General Hospital.

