8.2. Statistical and Analytical Plans

Our primary outcome will be attainment of beta-lactam therapeutic targets: 100%fT>MIC, 40-70%fT>5xMIC, 100%fT>5xMIC. Proportion of patients, who achieve beta-lactam therapeutic targets, during the first and subsequent TDM will be determined. For the group of patients, who require dose adjustments, after the 1st TDM and need further TDM, the proportion of patients who require dose increment and dose reduction, the number of TDM performed to achieve therapeutic target and the mean/median time required to achieve therapeutic target will also be evaluated.

Correlation of primary outcomes will be made to the following secondary outcomes.

- a. Mortality at the end of therapy and within 30-day mortality.
- b. Days to defervescence
- c. Days to resolution of white blood cell count, pro-calcitonin and C-reactive protein.

Any incidence of adverse effects related to beta-lactam therapy will also be reported and evaluated in correlation to beta-lactam levels.

For univariate analyses with binomial outcomes (e.g. mortality), Chi-square test or Fisher's exact test will be performed where appropriate. For univariate analyses with time-dependent outcomes (e.g. days to defervescence, days to resolution of inflammatory markers), Kaplan-Meier analysis will be performed. For univariate analyses with continuous outcome variables (e.g. APACHE II score, SOFA score), Student's t-test and Mann-Whitney-U test will be performed for parametric and non-parametric data respectively. Multivariate analyses will then be performed to include potential confounders such as APACHE II score, SOFA score, Charlson comorbidity index, use of beta-lactam as culture-directed therapy, presence of multi-drug resistant infection, and presence of concurrent infections requiring additional antibiotics. Logistic regression will be used for binomial outcomes (mortality) while Cox regression will be used for time-dependent outcomes (days to defervescence, days to resolution of inflammatory markers).

To evaluate population pharmacokinetics in various patient groups, a specialised pharmacokinetic software will be used to develop population pharmacokinetic models. Model simulation will then be performed to design empiric dosing recommendations to guide local practice.

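### Section 8.2 does not pre-specify the outcome's own starting value as a covariate in the Cox models for fever and marker resolution

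*Combined protocol and SAP*

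**What the plan says.** Section 8.2 lists among its secondary outcomes "Days to defervescence" and "Days to resolution of white blood cell count, pro-calcitonin and C-reactive protein". Each is to be related to attainment of the beta-lactam targets, first by Kaplan-Meier analysis and then in a multivariable model: "Cox regression will be used for time-dependent outcomes (days to defervescence, days to resolution of inflammatory markers").

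The adjustment set is given by way of example: "Multivariate analyses will then be performed to include potential confounders such as APACHE II score, SOFA score, Charlson comorbidity index", continuing with "use of beta-lactam as culture-directed therapy, presence of multi-drug resistant infection, and presence of concurrent infections requiring additional antibiotics". That makes six named covariates. No starting value of a marker or of temperature is named there or elsewhere.

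The data items exist. Under Data Collection, Section 5 lists "laboratory data (albumin, serum creatinine, procalcitonin, CRP, total white count") and "clinical data (temperature, blood pressure, heart rate, respiratory rate, mortality"). It sets no baseline day and no measurement schedule for them.

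The study is observational. Section 8.1 sets its size from the assay budget, without alpha, power or effect size.

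**The concern.** The time a marker takes to fall to a threshold depends on how far it has to fall. Take an assumed half-life of 2.5 days and a threshold of 10. A start of 300 then resolves about 4 days later than a start of 100, with an identical response to treatment.

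Nothing in the design balances starting values between patients who do and do not attain target. Imbalance is plausible on the protocol's own rationale. Section 1 says that critically ill, febrile neutropenic, burns and dialysis patients have variable pharmacokinetics, and Section 4.3 enrols such groups together. The type and severity of illness can therefore influence both attainment and initial inflammation.

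The results have a use beyond description. Section 2 makes the link between targets and clinical outcomes a secondary objective, and Section 1 intends to identify the best target for practice. A hazard ratio that partly reflects where patients started could mislead that choice.

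**Working it through.** **The plan's own figure.** 40,000 / 125 = 320 assays, and 320 / 4 = 80 patients. Both reproduce. There is no power or event calculation to check.

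**Distance to threshold (assumed inputs).** Time = 2.5 × log2(start / 10).
- Start 300: 2.5 × log2(30) = 12.3 days.
- Start 100: 2.5 × log2(10) = 8.3 days.
- Difference: 4.0 days.

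**Main simulation.** Only the 80 patients come from the documents; the rest is assumed.
- 40 attainers and 40 non-attainers; daily hazard = 0.1 × exp(ln(HR) × attainment − b × baseline in SD units).
- Censoring at day 30, about 70-77 events, two-sided 0.05, 1,500 runs per scenario. The Monte Carlo error at 5% is √(0.05 × 0.95 / 1500) = 0.6 points.
- b = 0.4 or 0.8. A severity score correlates 0 or 0.5 with baseline.
- Both models include attainment and the severity score. The second adds the baseline marker.
- HR above 1 means faster resolution in attainers.

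True HR 1.0, baseline difference 0.5 SD. Cells give the estimated HR and the false-positive rate:

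| b | Score correlation | Attainers lower, baseline omitted | Baseline added | Attainers higher, baseline omitted | Baseline added |
|---|---|---|---|---|---|
| 0.4 | 0 | 1.22, 12.3% | 1.01, 4.7% | 0.83, 11.9% | 1.00, 5.1% |
| 0.4 | 0.5 | 1.13, 7.6% | 0.99, 5.7% | 0.88, 8.1% | 1.01, 5.5% |
| 0.8 | 0 | 1.35, 22.1% | 0.99, 5.7% | 0.74, 23.0% | 1.00, 5.1% |
| 0.8 | 0.5 | 1.28, 16.1% | 1.01, 5.3% | 0.78, 18.1% | 1.01, 5.5% |

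True HR 2.0:
- Balanced groups: power 56-78% without the baseline value (HR shrunk to 1.67-1.92) and 82-85% with it. The loss runs from 84.2 − 78.4 = 5.8 points to 82.2 − 56.2 = 26.0 points.
- Attainers start higher: power 14-56% without, 80-82% with.
- Attainers start lower: rejection 90-92% without (HR inflated to 2.20-2.28), 79-82% with.

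**Second generating model.** This used exponential marker decline to a threshold of 10: half-life 2.5 days (log-SD 0.35), median start 120 (log-SD 0.8), 80 patients, half attaining, daily testing for 30 days, 1,500 runs. There was no true effect, and non-attainers started 0.5 SD higher.
- No covariates: HR 1.35, 26% false positives.
- One severity score added (400 runs): HR 1.29 and 20% at correlation 0.5; HR 1.21 and 15.5% at correlation 0.7.
- Log baseline as the covariate: HR 1.01, 7%.
- With log baseline, across imbalances of 0, 0.3, 0.5 and 0.8 SD, false positives were 8.8, 8.7, 7.4 and 8.2%. The slight excess over 5% is attributed to non-proportional hazards in this generating model.

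**Cost in model size.** Attainment plus six covariates is 7 terms; one more makes 8. At 80 events, events per term go from 80/7 = 11.4 to 80/8 = 10.0. At 56 events they go from 8.0 to 7.0.

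**The case against.** The strongest reply is that the covariate list is only illustrative. A reader might infer that the plan rules out baseline adjustment, and it does not. That objection stands, so the point is about pre-specification. An open list still does not settle the matter, because choosing this covariate after seeing the data invites selective adjustment.

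A reader might also take HR 1.35 with 26% false positives as the expected error. That result comes from a model with no covariates, whereas Section 8.2 plans to adjust for severity scores. Those scores reduce the bias, and more so the more closely they track the marker. In the scenarios run they did not remove it. How closely they would track it in this population is unknown.

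Two practical objections also stand. First, Section 8.2 defines neither a time origin nor resolution, and Section 5 is inconsistent. Its opening part counts 30 days from the start of beta-lactam therapy and follows to the latest listed event. Data Collection counts from study entry and stops at the earliest. Patients are already receiving the drug when enrolled, so a value taken at study entry may reflect drug exposure, and adjusting for it could remove part of the effect under study. Second, haematology and oncology patients are enrolled, and a low white count recovers upwards. A single log white count term would not suit them.

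Finally, the simulations are kinder than the study may be. They give every patient a starting value, but Section 5 promises no baseline draw. Repeat monitoring also uses up the 320 assays, so there may be fewer than 80 patients.

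**Conclusion.** The concern holds in a limited form. The plan names no outcome-specific starting value for four non-randomised time-to-event comparisons, although the data items are collected. Bias arises only if starting values differ by attainment beyond what APACHE II and SOFA explain, and its direction cannot be predicted.

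For a 0.5 SD difference and no true effect, the main simulation gives the range 1.13-1.35 or 0.74-0.88. Adding the baseline value brings the estimate back to about 1.0. Every input except the 80 patients is assumed, and the documents support no single magnitude.

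A reader might infer that omission always loses power. It does so when groups are balanced or attainers start higher. When attainers start lower, rejection rises and the effect is overstated. Nor does the plan make any power claim that this would contradict.

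The affected analyses are secondary. The primary outcome, the proportion attaining target, does not depend on these models. The change is worth making before analysis because it is cheap and specific.

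**What to change.** In Section 8.2:
- Add to each Cox model the starting value of that outcome's own marker: log CRP, log procalcitonin or temperature. Model white count so as to allow for patients who start low.
- State one time origin and take the value at or last before it. The start of beta-lactam therapy is preferable, because the value then precedes drug exposure.
- Restrict each model to patients whose marker is abnormal at that origin, and define resolution.

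In Section 5, reconcile the two statements of when follow-up starts and ends, since the origin decides which value counts as the starting one.

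The costs are modest but go beyond one sentence. Each model gains a term, which matters with about 80 patients. Patients with no starting value leave that marker's model. Section 5 begins data collection only after consent, so the plan should say whether earlier values already in the medical record may be used. Attainment is assessed after therapy starts, so with that origin patients should enter the risk set only when attainment is known. Dropping one of the two severity scores to make room is optional; the documents do not show that they overlap.

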9. DIRECT ACCESS TO SOURCE DATA/DOCUMENTS

The investigator(s)/institution(s) will permit study-related monitoring, audits and/or IRB review and regulatory inspection(s), providing direct access to source data/document.

10. QUALITY CONTROL AND QUALITY ASSURANCE

Standardised data collection form will be used to ensure accuracy of data collected. The investigators will evaluate data quality every 3 months.

11. ETHICAL CONSIDERATIONS

This study will be conducted in accordance with the ethical principles that have their origin in the Declaration of Helsinki and that are consistent with the Good Clinical Practice and the applicable regulatory requirements.

This final Study Protocol, including the final version of the Participant Information and Consent Form, must be approved in writing by the Centralised Institutional Review Board (CIRB), prior to enrolment of any patient into the study.

The principle investigator is responsible for informing the CIRB of any amendments to the protocol or other study-related documents, as per local requirement.

11.1. Informed Consent

Patients eligible for the study will be first approached by their treating physicians for consent to be referred to the study team.

For critically ill patients who are unable to give consent, documentation of mental capacity will be made by primary physician and consent from patients' spouse, parent, guardian or LAR will sought before study team approach them. Informed consent will be obtained from the spouse, parent, guardian or LAR using the substituted consent form. Once patient has regained capacity to give informed consent, their consent for continued participation will be obtained using the continued participation consent form.

Informed consent will then be taken by a designated member of the study team in a quiet area at an appropriate time when the patient or his / her spouse, parent, guardian or LAR will not be interrupted by other healthcare workers, patients or visitors. The objectives, study procedures, risk and benefits will be explained and any questions will be answered.

Informed consent will be obtained from English-speaking patients and/or his/her representatives only.

All informed consents will be held in the presence of a witness. All patients will be given sufficient time to make a decision.

While obtaining and documenting informed consent, the study team members will comply with the SGGCP guidelines and to the ethical principles that have their origin in the Declaration of Helsinki.

11.2. Confidentiality of Data and Patient Records

Informed consent process will be done at patient bedside. If more privacy is warranted, consent

will be taken in a single room or treatment/counseling room.

All blood samples will be labelled by a subject code by the study team (i.e. no patient identifier will be used).

Data will be stored in a password-protected electronic database and only study team members will have access to data. Identifiers will be stored separately from collected data. Data collection forms will not contain identifiers (e.g. NRIC, name, date of birth). All hardcopy data collection forms and consent forms will be stored under lock and key in the cupboard at [name] of Pharmacy department in Singapore General Hospital. Only the PI and designated study members have access to the locked cupboard.

